View: 2 Study Objectives & Design

Study Summary**1.0 Funding End Date:****2.0 * Abstract. Please provide a brief description of the study.**

Stroke is the leading cause of neurological disability in the veteran population and problems with arm movement are a major cause of loss of functional ability. The costs of rehabilitation are significant and effectively limit therapy to the first few months after stroke onset. Recent results show clearly that patients with chronic stroke (> 6 months) benefit from intensive arm practice. Robot assisted therapy followed by task related training offers a cost-effective approach to this type of practice that also results in better arm function in daily life. A previous study has shown that it is possible to predict who will benefit from this kind of treatment, specifically what individual characteristics are related to a clinically meaningful improvement in arm movement. This next phase of the study will test whether the prediction method is reproducible and independent of the type of robot being used. It will also expand knowledge of how the brain area most important for movement changes its connections with other brain areas and the muscles in the arm.

3.0 * Describe the study objectives. Please include primary aim and hypothesis, if applicable any secondary aims and hypotheses.

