Chronic upper extremity dysfunction after stroke is a leading cause of disability and has been the target of many therapeutic methods that involve repetitive task practice. Clinical trials of intensive practice-based interventions have demonstrated significant changes in mean impairment in a group, but variable effects among individuals, with clinically significant improvements in only a fraction of the population. This is true of our previous Merit Review study, which showed good mean gains in several areas, and about half of participants having clinically significant changes in the primary outcome of motor impairment. The basis for these variable responses is not known, i.e. we do not know the biological mechanisms that moderate response to these standardized interventions. And while recovery of function is associated with normalization of brain network interactions and task-related brain activation, the causal role of these changes is not well understood. In our current project period, we are continuing to address both issues with construction of a predictive model that uses demographics, functional status, genomics, neurophysiology, neuroanatomy, and other potential biomarkers to predict the likelihood of a clinically significant change in impairment at the end of the intervention.

Our long-range goal is the prescriptive application of intensive task practice to veterans who have suffered a stroke, maximizing the cost-benefit ratio. We therefore plan to externally validate the predictive value of biomarkers as incorporated in the model resulting from our previous chronic stroke robotic rehabilitation trial. We will not only validate the predictive model in a new cohort, we will now quantify the *changes* in functional connectivity of the affected hemisphere's primary motor cortex with other brain areas and with the spinal cord, in order to uncover the mechanisms by which intensive task practice leads to increased motor ability. We will continue to use an effective intervention for individuals with chronic stroke, robotic training

with transition to task practice (Robot + TTT,) now focusing on use of an *exoskeleton platform*, which has already been part of our intervention. We propose the following two specific aims in the proposed renewal of this award:

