1. To validate a predictive model based on baseline measures of biological and functional biomarkers. *Working hypothesis: Baseline factors that include functional and physiological status will predict clinically significant responses to therapy.* Change from use of end-effector and exoskeleton robots to solely exoskeleton will not significantly affect the prediction model. The rationale for the hypothesis is that the effects of assisted repetitive task practice is not dependent on a particular technology but does depend on a biological substrate. Expected outcomes: The predictive model will be externally validated, a receiver operating curve described, and the intervention and model validated on an exoskeleton platform for delivering therapy.

2. To identify the changes in the input and output of the affected primary motor cortex associated with change in motor impairment. *Working hypothesis: Increased input into the motor cortex, increased output from the motor cortex, or both, underlies the treatment effect of repetitive task practice.* Normalization (increase) in connectivity of affected primary motor cortex to other motor brain areas of both sides of the brain will be associated with reduction of motor impairment. In a subpopulation of treatment responders an increased effectiveness of the motor cortex in directly activating muscles will be demonstrated. Expected outcome: The causal role of task practice in changing a brain region's connectivity will be known, with potential uses as a surrogate measure of outcome in rehabilitation trials. Resting state BOLD MRI, transcranial magnetic stimulation, and clinical electrophysiology will be used to provide data regarding the mechanisms of training-related gains.

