When we have completed the above aims, we will have a validated algorithm by which a set of baseline variables (biomarkers) can be used to inform both the clinician and patient regarding the likelihood of successful training, in an appealing exoskeleton robotic rehabilitation platform, for upper extremity disability in the chronic period after stroke. This algorithm can be modified to consider those biomarkers that are more practical in VA clinical settings. We will also extend mechanistic knowledge about the response to intensive training on brain connectivity, which has been noted to be altered after stroke and which may relate to learned non-use of the affected limb and loss of spinal response to descending input. We will have new efficacy data on the use of assisted mass practice followed by assisted task practice on multiple dimensions of functioning and disability, including use of the arms in daily life.

4.0 * Provide a summary of the background of the study, and explain how this research will contribute to existing knowledge. Describe previous studies that provides a basis to show that the proposed research can be carried out without undue risk to human subjects.

Stroke is the leading cause of long-term disability [1] costing an estimated \$38.6 billion a year [2] and stroke-related disability is becoming more prevalent [3], even as overall rate of stroke is in slight decline. Recent evidence indicates that the brain can remodel after stroke, even years later, through neuroplasticity (including changes in excitability and synaptic strength) and synaptogenesis [4-6]. Behavioral remodeling also occurs and allows compensatory movement patterns to accomplish

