task goals [7-9]. Interventions incorporating strategies of task specificity, challenge, and repetition appear to be key factors in promoting these two types of remodeling and are central elements in rehabilitation of motor weakness following stroke [11]. Since our initial project period, the value of robot-assisted therapy to improve upper extremity function has become more established but there are still questions about many aspects of implementation, including patient selection, dose, and type of treatment [12]. There are two basic types of rehabilitation robots, *endeffector*, in which the patient engages with the tip of the limb, and *exoskeleton*, in which a powered framework encloses the limb. Both types have demonstrated efficacy [13] with some potential advantage in full use of exoskeleton capabilities in training joint coordination [14], and we have used both types in our ongoing study. Robot-assisted and other types of upper extremity treatment studies in chronic stroke report relatively modest *average* gains in motor function that typically fail to translate into meaningful change in everyday use of the paretic arm [15]. This has prompted us to directly address issues of predicting response, promoting and measuring translation to daily use and determining optimal scheduling for that therapy. Therefore, there is now a critical need for research that: 1. predicts response to hybrid robotic and functional task oriented therapies in chronic stroke and 2. determines the brain mechanisms of response to such therapies so that we better understand why such therapies work for some, but not all, stroke survivors.

5.0 * Describe the overall significance of the research in terms of the problem to be studied and potential findings, as well as its relevance to the care of veterans, the VAPHS, and the VHA:

Importance and Impact

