If yes, please indicate which time points are considered usual care and which are considered research.

2.4 If there is more than one standard, does VAPHS limit which one is followed (e.g. warfarin use for atrial fibrillation vs. one of the newer anticoagulants).
 Yes **No**

If yes, please explain:

3.0 * **Does clinical expertise need to be enlisted?**
 Yes **No**

If yes, please provide the provisions for enlisting the services of a clinician with appropriate expertise and privileges to perform duties, if the investigator is not a clinician [i.e. reviewing the data, adverse events, and new study findings; also making required decisions to protect the health of the subject (e.g., stopping the participant’s involvement in the study or determining when to notify the subject or the subject’s health care provider of information that may affect the health of the subject)]:

4.0 Please upload any surveys, questionnaires, and data collection forms.

Document	Description	Version Number
View ARAT Scoring(0.01)		0.01
View Demographics(0.01)		0.01
View Dynamometry and ROM Scoring(0.01)		0.01
View Finger Assessment Form(0.01)		0.01
View Fugl-Meyer Scoring(0.01)		0.01
View Inclusion Exclusion Checklist(0.01)		0.01
View Medical History Form(0.01)		0.01
View Stroke History Form(0.01)		0.01
View Stroke Impact Scale(0.01)		0.01
View Wolf Scoring(0.01)		0.01

ID: Pro00003161

View: 4.1 Research study methods: analysis Plan

1.0 * **Please describe the analysis plan for the study** (*it is acceptable to refer to the sponsor/multi-site protocol for section if applicable*):

Analysis Plan for Aim #1.

We will determine the receiver operating curve (ROC, sensitivity vs 1-specificity) of the predictive model for the primary outcome, a (positive) change in FMA of greater than four points at 12 weeks. (A five-point change in FMA is a MCSD [34].) The ROC will be compared to the SRT4 model [35]. With our proposed sample size of 64 subjects and 12% attrition rate, we expect to have 57 subjects completing the study, a validation set of similar size to the original set from which the model was derived.

Further analysis, validation and refinement of the predictive model will be performed using the random decision forest technique [36]. This would also result in an algorithm like the PREP [30] that can be used for step-wise decision-making about embarking on the 12-week program of robot+TTT.

Analysis Plan for Aim #2.

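### Aim 1 assesses the model by ROC/AUC alone, so the stated analysis cannot detect uniform over- or under-prediction of response, including any that follows the change of robot

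*Combined protocol and SAP*

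**What the plan says.** All references are to the combined protocol and SAP.

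- **Section 4.1, Aim #1:** "We will determine the receiver operating curve (ROC, sensitivity vs 1-specificity) of the predictive model for the primary outcome", the outcome being an FMA gain of more than four points. The ROC is then compared with the SRT4 model, citing reference 35, a method for comparing areas under ROC curves.
- **Section 4.1, Aim #1, next step:** "Further analysis, validation and refinement of the predictive model will be performed using the random decision forest technique". The text does not say which data train the forest and which test it.
- **Section 2, item 3.0, expected outcome of Aim 1:** "The predictive model will be externally validated, a receiver operating curve described".
- **Section 6, item 4.0:** the Aim 1 sample size rests only on the standard error of the AUC with 57 completers.
- **What is promised (section 2, item 3.0):** a model to "predict the likelihood of a clinically significant change in impairment at the end of the intervention", and at the end "we will have a validated algorithm by which a set of baseline variables (biomarkers) can be used to inform both the clinician and patient" about the likelihood of successful training.
- **The robot claim:** the working hypothesis is "Change from use of end-effector and exoskeleton robots to solely exoskeleton will not significantly affect the prediction model" (section 2, item 3.0). The abstract says that the study will "test whether the prediction method is reproducible and independent of the type of robot being used".

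The text contains no comparison of observed with predicted response, no calibration measure, no Brier score and no cut-off.

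**The concern.** A likelihood of success has two properties that need checking: whether it orders patients correctly (discrimination) and whether its level is right (calibration). The ROC and its area address only the first. Any order-preserving distortion of the predictions leaves the ROC identical.

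Two stated goals depend on the second property. One is telling a clinician and patient how likely success is. The other is the claim that moving to exoskeleton-only training leaves the prediction model unaffected. If response rose or fell across patients without reordering them, the ROC comparison would show nothing. A good AUC could then be reported as validation, and as evidence that the robot change does not matter, without predicted and observed response having been compared.

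**Working it through.** **1. The plan's own figures.** Completers: 64 × 0.88 = 56.3, stated as about 57. The Hanley–McNeil standard error (the plan's reference 10) is

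SE² = [A(1−A) + (n₁−1)(Q₁−A²) + (n₀−1)(Q₂−A²)] / (n₁n₀), with Q₁ = A/(2−A) and Q₂ = 2A²/(1+A).

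At A = 0.70, n₁ = 19, n₀ = 38: Q₁ = 0.538, Q₂ = 0.576, and SE = √[(0.21 + 18×0.0485 + 37×0.0865)/722] = 0.077.

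| Responders | AUC 0.7 | AUC 0.8 | AUC 0.9 |
|---|---|---|---|
| 33% | 0.077 | 0.067 | 0.050 |
| 50% | 0.0695 | 0.059 | 0.043 |

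This agrees with the statement that the SE is below 0.07 except at AUC 0.7 with 33% responders. The table itself is missing from the text, so this grid is an assumption. The precision claim is sound, but it concerns discrimination only.

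**2. Rank invariance.** Simulated outcomes with 50% responders were scored with the true risk, with a logit-shifted risk and with the cubed risk. Mean predicted risk was 0.50, 0.33 and 0.17; the AUC was 0.6998 each time.

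**3. Illustrative shift.** Inputs:
- AUC 0.70 and 33.3% responders, from section 6, item 4.0.
- 50% for the statement in section 2, item 3.0 that roughly half responded in the previous study. That sentence does not give its threshold.
- Assumed: equal-variance binormal score, baseline predictor distribution unchanged, true response shifted by a constant on the logit scale, n = 57. Predictors are measured before training, so the robot used cannot change their distribution.

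The separation is d = √2 × z(0.70) = 1.414 × 0.524 = 0.742. The calibrated prediction is p(x) = expit[logit(p₀) + dx − d²/2]. The true response is expit[logit p(x) + δ], with δ solved so that the mean equals the new rate; δ is about −0.79 or +0.79.

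| | Calibrated 50%, true 33.3% | Calibrated 33.3%, true 50% |
|---|---|---|
| Predicted responders of 57 | 28.5 | 19.0 |
| Observed responders of 57 | 19.0 | 28.5 |
| Gap | 9.5/57 = 16.7 points | 16.7 points |
| AUC | 0.70 | 0.70 |
| Brier score, unchanged model | 0.226 | 0.249 |
| Brier score, recalibrated | 0.197 | 0.220 |

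**4. If the output is a class.** Cut at the midpoint d/2, the calibrated model has sensitivity = specificity = Φ(d/2) = 0.645. A predicted responder then succeeds with probability 64% (calibrated at 50%) or 48% (calibrated at 33.3%). After the shift these become about 46% and 66%. Sensitivity and specificity also move at that cut, to about 0.69/0.60 and 0.59/0.69.

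**5. What each check would detect.** In simulations with predicted risk 50% and true response 33% or 40%, an AUC comparison between two independent sets of 57 rejected in about 4–6% of runs, its false-positive rate. Under the model of step 3, a two-sided 5% test of observed minus predicted responders has power of about 0.78–0.80 for the 16.7-point shift and about 0.36–0.40 for a 10-point shift. If the shift comes from case mix (score distribution fixed within responders and non-responders), the gap narrows to about 15 points (27.3 against 19.0, or 20.1 against 28.5), and power falls to about 0.66–0.69 and 0.29–0.33.

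**The case against.** **The plan already validates externally.** It commits to testing the earlier trial's model in a new cohort, separate from the derivation set. This stands: the ROC step is a genuine external validation of discrimination. It does not cover the level of the predictions.

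**The tool may give a class.** Section 4.1 mentions a step-wise algorithm like PREP, and the output type is not stated. That also stands, but step 4 shows that the meaning of a favourable class moves too.

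**Other sources may say more.** This is a form field; the grant application and the SRT4 model specification are not in the text. The point is therefore limited to the analysis stated here.

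**Fifty-seven subjects are too few.** Precision is indeed poor. That argues for reporting an interval, not for omitting the comparison.

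**Stronger readings that the documents do not support:**
- *The robot change will shift response.* The background mentions "some potential advantage in full use of exoskeleton capabilities in training joint coordination", which concerns joint coordination rather than FMA response, and the same sentence says that both robot types are efficacious.
- *The two responder shares show that a shift has occurred.* Roughly half and 33% both refer to earlier work, one without a stated threshold. They serve here only as illustrative values.
- *A calibration check would test the robot effect.* The study has one arm and SRT4 is a historical comparison. Cohort differences, assessors or error in the SRT4 model's intercept could produce the same gap.
- *The random forest will be tested on its own training data.* The text does not say so. Training on SRT4 and testing on SRT5 would be independent.

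**Conclusion.** The point holds as a gap in the stated analysis. ROC/AUC is the only performance measure named for Aim 1, and it cannot show uniform over- or under-prediction. In the illustration a 16.7-point error in the mean predicted response leaves the AUC at 0.70 and adds about 0.029 to the Brier score (0.226 − 0.197; 0.249 − 0.220). The size rests on the assumed AUC, responder rates and constant logit shift; the rank argument needs none of them. The plan should be changed, because its promised likelihood and its robot claim both go beyond what an ROC can support. The random-forest gap is secondary and concerns reporting only.

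**What to change.** 1. Apply the SRT4 model unchanged (predictors, coefficients, any cut-off) to SRT5.
2. Beside the AUC, report calibration-in-the-large: observed versus predicted responders with a 95% CI. If the model gives a class, report observed responders per predicted class with exact 95% CIs. Keep the Brier score and calibration slope descriptive. Label any recalibration as a model update.
3. Do not conclude from the ROC comparison alone that the robot change leaves the model unaffected. Report calibration-in-the-large with it, and state that a shift in a one-arm study with a historical comparison shows that predictions are off, not that the robot caused it.
4. State which data train and test the random forest. If SRT5 data fit or refine it, report it as exploratory with out-of-bag or optimism-corrected performance, and keep the word validated for the unchanged SRT4 model.

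**Cost:** a few lines of plan and computations on data already collected; no extra subjects or visits. The price is imprecision. The observed rate is known only to 1.96 × √[p(1−p)/57], which is ±12 points at 33% and ±13 at 50%. The rate within a predicted-responder class of about 26 to 29 people is known only to about ±18 points (1.96 × √[0.46×0.54/28.5] = 0.18). With the power given above, a non-significant result must not be read as good calibration.

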The primary purpose of the current proposal is to externally validate predictors of response to Robot + TTT (transition-to-task) therapy in the chronic stroke population. By doing so, we will validate biomarkers and algorithms for a predictive model to guide matching of patients to a therapy based on residual neural and motor function and other measurable factors. We have been contributing to understanding the mechanisms of recovery specifically by relating baseline clinical, neurophysiological and kinematic markers to functional outcomes. We are now proposing to go beyond this contribution by measuring specific changes in connectivity of the primary motor cortex, the hub of voluntary movement function in the human brain.

While we, and others, have as a goal personalized treatment during the *sub-acute* period when spontaneous recovery, optimal neuroplasticity and available rehabilitation coincide, the field has been turning to **chronic** populations for a few reasons. First, doing so addresses the problem of an exponential growth in individuals aging with disabilities from stroke. Strokes are occurring earlier in the lifespan [16] and individuals live longer with stroke [17] therefore causing increased costs to society as a public health concern as well as increased costs to the individuals who face more years with a lower quality of life. Since it is known that neuroplasticity continues across the lifespan [18] and that rehabilitation can be effective years after the stroke e.g. [19], validating biomarkers and algorithms that *best match individuals with a specific therapy will maximize recovery of function and reduce health care resource utilization over the long term. Second, providing further evidence*

for optimal use of robotic therapy in the chronic period may provide an impetus for the installation of robots and other arm exercise programs into health clubs and veteran's service organizations where rehabilitation and exercise can usefully combine.

Impact on Health Care Delivery for Veterans:

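### No Aim 1 analysis compares the full model with a clinical-only model, so the study cannot show that the biological markers add predictive value

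*Combined protocol and SAP*

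**What the plan says.** **The promise.** View 2, item 3.0 (study objectives): "We therefore plan to externally validate the predictive value of biomarkers as incorporated in the model" from the earlier trial. View 2, item 5.0 (Importance and Impact): "we will validate biomarkers and algorithms for a predictive model to guide matching of patients to a therapy". Aim 1 itself is worded as "To validate a predictive model based on baseline measures of biological and functional biomarkers". The predictors are listed as "demographics, functional status, genomics, neurophysiology, neuroanatomy, and other potential biomarkers". Item 3.0 adds, of the period after the aims are complete: "This algorithm can be modified to consider those biomarkers that are more practical in VA clinical settings".

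**The analysis.** View 4.1, item 1.0 gives three steps for Aim 1:
- "We will determine the receiver operating curve (ROC, sensitivity vs 1-specificity) of the predictive model for the primary outcome", where the outcome is an FMA gain of more than four points at 12 weeks;
- a comparison of that ROC with the SRT4 model, citing the DeLong method for correlated ROC curves;
- a random forest for further validation and refinement, intended to lead to a step-wise decision algorithm.

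No clinical-only comparator, nested comparison, variable-importance measure or criterion for calling a model or marker validated is stated. The sample-size justification (View 6, item 4.0) for Aim 1 rests on the standard error of the whole-model AUC with 57 completers.

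**The concern.** One AUC for a combined score does not show which inputs produce the discrimination. If demographics and baseline arm function carry all of it, the planned ROC can still look good. The SRT4 comparison sets one whole model against another, so it has the same limit. The random forest could in principle rank predictors, but no ranking or reduced model is specified, and refitting in the new cohort is not external validation. Aim 2 does not fill the gap: it correlates change in physiology with change in FMA, and baseline physiology with baseline function. Neither asks whether baseline markers predict response once clinical measures are known.

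Whether TMS and MRI belong in the algorithm decides what equipment a clinic needs to use it. TMS is also the stated reason for the greater-than-minimal-risk classification (View 7), and each MRI takes about 1.5 hours (View 4). Adapting the algorithm to more practical markers needs the same information.

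**Working it through.** **1. The plan's own figure.** Hanley-McNeil standard error, with Q1 = A/(2−A) and Q2 = 2A²/(1+A):

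SE = √{[A(1−A) + (n1−1)(Q1−A²) + (n0−1)(Q2−A²)] / (n1·n0)}

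| Responders (of 57) | AUC 0.70 | AUC 0.80 | AUC 0.90 |
|---|---|---|---|
| 33% (19 v 38) | 0.077 | 0.067 | 0.050 |
| 50% (28 v 29) | 0.070 (0.0697) | 0.060 | 0.043 |

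View 6 says the SE is below 0.07 except at AUC 0.7 with 33% responders. That reproduces on this grid. The grid is assumed, because the table is not in the text. Nothing in this point depends on a stated figure being wrong.

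**2. Can the whole-model AUC look good when the markers are useless?** Assumptions, none given in the documents: clinical-only AUC 0.70; markers are pure noise added to a unit-SD clinical score with relative weight w. Then, under a binormal model, AUC = Φ(0.5244/√(1+w²)), where 0.5244 = Φ⁻¹(0.70). The chance that the 95% interval lies above 0.5 is about Φ((AUC−0.5)/SE − 1.96). With 19 v 38:

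| w | AUC | SE | (AUC−0.5)/SE | By formula | By simulation |
|---|---|---|---|---|---|
| 0 | 0.700 | 0.0770 | 2.60 | 74% | 73% |
| 0.3 | 0.692 | 0.0775 | 2.48 | 70% | 68% |
| 0.5 | 0.680 | 0.0783 | 2.31 | 63% | 63% |
| 0.75 | 0.663 | 0.0793 | 2.05 | 54% | 52% |
| 1.0 | 0.645 | 0.0801 | 1.81 | 44% | 43% |

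The simulation used 4,000 trials per row, a correlation of 0.428 between clinical score and FMA change, the top 19 of 57 as responders, and DeLong standard errors. With 50% responders the formula gives 82% at w = 0 and 51% at w = 1. The exact figure depends on w; the conclusion does not.

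**3. What a paired comparison would give.** SE(difference) = √(s0² + s1² − 2ρ·s0·s1), with AUC 0.70 against 0.75 and the correlation ρ between the two AUC estimates assumed at 0.5 to 0.8.
- Tightest case, 57 participants, 50% responders, ρ = 0.8: s0 = 0.0697, s1 = 0.0652, SE = 0.0428, half-width 1.96 × 0.0428 = 0.08.
- Widest case, 45 participants (assumed number with TMS and MRI data), 33% responders, ρ = 0.5: s0 = 0.0869, s1 = 0.0822, SE = 0.0846, half-width 1.96 × 0.0846 = 0.17.

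Simulated power of the paired DeLong test at n = 57, from a clinical-only AUC of 0.70, for 33% and 50% responders: 15% and 17% for a full-model AUC of 0.75; 34% and 37% for 0.80; 57% and 63% for 0.85.

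**4. Regression on continuous FMA change.** The coefficient of a biomarker score, adjusted for a clinical score that correlates 0.323 with change (two-sided 5%, simulated):

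| n | Correlation between scores | Power, marker r = 0.3 | Power, marker r = 0.4 |
|---|---|---|---|
| 57 | 0 | 67% | 91% |
| 57 | 0.5 | 24% | 57% |
| 45 | 0.5 | 19% | 50% |

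Here r is the marker's marginal correlation with change. Power is good only if the two scores are unrelated. The plan gives no reason to assume that, since Aim 2 will itself correlate baseline physiology with baseline motor function.

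**The case against.** The strongest reply is that Aim 1 promises to validate a model, and a whole-model ROC does that. The objectives tie the biomarker promise to the markers as they sit in the earlier model, and Aim 1 counts functional measures as biomarkers. This is fair, and it limits the point to the biological markers. It does not remove it: on that definition baseline function alone could carry a biomarker validation, and the Importance and Impact section promises to validate biomarkers as well as algorithms.

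Two stronger readings are tempting and unsupported. A reader might infer that the ROC is the only Aim 1 analysis; the plan also has the SRT4 comparison and the random forest. A reader might infer that the plan would declare useless markers validated; it sets no success rule and treats the AUC as an estimate with a standard error. The test against 0.5 used above is a yardstick chosen for this check, so the most that can be said is that a good AUC could be misread.

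Three practical objections also stand. The SRT4 model's terms and form are not in the documents, so it may not split into parts. People ineligible for TMS or MRI remain in the study (View 6.1, item 3.0), so the comparison will probably have fewer than 57. Genomics is a named input, yet the evaluations in View 4 describe no genomic sampling.

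**Conclusion.** The point holds in this form: as written, Aim 1 cannot show that the biological markers add predictive value beyond demographics and baseline function, although the document promises to validate the predictive value of biomarkers. The ROC remains a sound measure of the whole model's discrimination.

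The 43% to 73% range rests on an assumed clinical-only AUC of 0.70, 33% responders, 57 completers and marker weights from 1 down to 0. It illustrates that a good overall AUC is uninformative about the markers; it is not a prediction for this trial. A reader might also conclude that a significance test of the markers should decide whether they may be called validated. The power figures do not support that: such a test could easily miss useful markers. The change is a worthwhile, inexpensive improvement and corrects no error in the plan's figures.

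**What to change.** In View 4.1, Analysis Plan for Aim #1:

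1. Prespecify a clinical-only comparator: the SRT4 model's demographic and functional terms if they can be separated, otherwise a clinical-only model fixed from SRT4 data before SRT5 outcomes are analysed.
2. In SRT5 participants with TMS and MRI data, report the AUC of the full and clinical-only models and their paired difference with a DeLong 95% interval, as an estimate. The plan already cites this method.
3. As a supportive analysis, regress continuous FMA change on the clinical score and the biomarker score, and report the biomarker coefficient with its interval. Do not use it as a gate.
4. Describe the overall AUC as validating the model as a whole, and word any statement about the biological markers by the comparison.

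The cost is a few lines of text and two small analyses, with no new visits or measurements for the TMS and MRI markers. The interval will be wide (half-width roughly 0.08 to 0.17 under the assumptions above) and power for a modest gain is low, so the plan should say that a null result is not proof of no value. The biomarker claim may also end up weaker than the overall AUC suggests.
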